6.11.2 Efficacy Analysis Methodology

6.11.2.1 Analysis of Primary Efficacy Variable

The primary comparison of progression-free survival between KW-0761 and vorinostat will be performed on the ITT set based upon the results of the on-site Investigator's assessment using a stratified Log-rank test at the one-sided 2.5% significance level. Stratification is done by disease type (MF or SS), disease stage (IB/II or III/ IV), and region (U.S., Japan, and Rest of World). A Cox proportional hazard model with treatment, disease type, disease stage, and region (U.S., Japan, and Rest of World) as covariates will be used to assess the magnitude of the treatment difference in PFS. The hazard ratio along with the 95% confidence interval obtained from the Cox proportional hazard model will be presented. Additional analyses may be performed adjusting for treatment and other baseline characteristics.

The median PFS and the 2-sided 95% confidence interval for each treatment will be estimated using the Kaplan-Meier survival analysis methods. Kaplan-Meier estimate of PFS rates and the corresponding 95% confidence interval will also be provided for each treatment arm by 6 months intervals. Plots of the Kaplan-Meier estimate of the survival distribution function over time for PFS will be presented by treatment arm.

The primary analysis of PFS will be performed when 255 total PFS events have been observed or 24 months after the last randomized subject's first dose, whichever comes first.

6.11.2.2 Sensitivity Analyses of Primary Efficacy Variable

Three sensitivity analyses will be performed for PFS during randomized treatment period based on the on-site Investigator's assessment and the ITT Set using the following definitions:

- 1) Sensitivity Analysis 1: PFS is defined as the time from the day of randomization to a treatment arm until documented progression in any compartment based on the Investigator's assessment per CTCL response criteria or death due to any cause provided that death is not more than 8 weeks after the last post-baseline tumor assessment or the last dose of study drug (if the subject did not have any post-baseline tumor assessment).

Using this definition, the disease progression reported during the follow-up period would not be considered as an event in the sensitivity analysis, but would be a censored value on the day of the last tumor assessment.

- 2) Sensitivity Analysis 2: PFS is defined as the time from the day of randomization to a treatment arm until the earliest date of documented progression in any compartment based on the Investigator's assessment per CTCL response criteria, or clinical progression at the end of the randomized treatment, or documented disease progression reported during the follow-up period, or death due to any cause.

Using this definition, clinical progression noted at the end of the randomized treatment would be considered as an event in the sensitivity analysis.

- 3) Sensitivity Analysis 3: An additional worst-case sensitivity analysis will be performed based on the ITT Set using the following definition:

PFS is defined as the time from the day of randomization to a treatment arm until documented progression or death due to any cause. The date of documented disease progression will be the earliest date of disease progression in any compartment based on the Investigator's assessment per CTCL response criteria or disease progression reported during the follow-up period. For assessments where progression is reported by the investigator but is **not** confirmed by the IR, the progression date will be set to the last tumor assessment plus one day in the KW-0761 treatment arm and will be censored in the Vorinostat treatment arm.

The same censoring rules as described in Section 6.11.1.1 will be used for the sensitivity analyses.

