5.1.4.1 Independent Review of Progression

A blinded Independent Review of response data for each subject will be performed to make a determination regarding progression and the date of progression. The nodal and visceral compartments evaluation will be based upon radiologic data. The independent radiology review of radiographic exams will provide an assessment of tumor response and progression for all subjects. A separate radiology charter will detail the roles and responsibilities of the radiology reviewers and how the reads will be performed. An independent reviewer (IR) will assess PFS based on date of progression or death, whichever comes first. For this assessment the independent reviewer will be supplied the results of the independent radiology review, the mSWAT score for each subject, as assessed by the investigator, and the results of central flow cytometry in order to assess blood response, and date of death for subjects who died before progression.

Secondarily, the IR will review the date of any objective responses (CR or PR) for each subject.

The independent review charter identifies the data package that the Independent Reviewer receives to review responses for each subject with baseline and at least on post-baseline measurement in the study.

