6.3 Determination of Sample Size

Since the primary endpoint is PFS, the reference median PFS for vorinostat is assumed to be 169 days.⁵ The median PFS for KW-0761 therapy is targeted for 254 days, a 50% improvement over this reference median. For a 24-month accrual and 12 month follow-up on the last subject dosed, Table 10.3-1 of the protocol gives the power and the number of PFS events required to show superior PFS for KW-0761 therapy over vorinostat at the one-sided

0.025 significance level. The Intent-to-Treat (ITT) set is used for this primary analysis. The same analysis conducted using the Efficacy Evaluable set is considered secondary.

Under these assumptions, for the ITT population, a total of 255 PFS events will give 90% power. For this study, the final primary analysis comparing PFS between treatment groups will not be conducted until 255 PFS events occur or until a maximum of 24 months after the last randomized subject's first dose, whichever comes first. In the event that the study is stopped prior to 255 PFS events being observed, the primary test will be performed at less than 90% power under the current assumptions according to Table 10.3-1 in the protocol.

Each of these calculations used a log-rank test to compare the two survival curves. Sample size calculations were computed using SAS software version 9.3 using PROC POWER, Twosamplesurvival test = logrank.

The total sample size of 288 represents the approximate number of subjects that may be necessary for 255 PFS events to occur within the projected 36 months of the trial. If a 10% inflation factor is applied to this total (about 29 subjects) to take into account those subjects that may be lost to follow-up prior to documented progression, a total of 317 enrolled subjects may be necessary in order to observe 255 PFS events.

The observed rates of PFS events, recruitment, and drop-outs will be monitored throughout the study and may be used to alter the number of sites, the accrual period, and the follow-up period to achieve the required 255 PFS events in a timely manner. If the 255 PFS events are not observed within 36 months from the start of enrollment the study will be stopped at approximately 24 months after the last randomized subject's first dose.

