- For subjects not known to have died or have documented progression as of the end of the study, the PFS time will be censored at the date of the last post-baseline tumor assessment (from any compartment).

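### Sensitivity Analysis 3 is labelled worst-case, but it ignores KW-0761 progressions that only the independent reviewer calls or dates earlier, and its KW-0761 event date is not tied to the progression visit

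*SAP*

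**What the plan says.** The trial is open-label (Protocol 4.1) and the primary endpoint is PFS by the on-site investigator (SAP 6.11.1). A blinded IR also determines progression. According to SAP 5.1.4.1 the IR works from an independent radiology read, central flow cytometry and "the mSWAT score for each subject, as assessed by the investigator".

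SAP 6.11.2.2 lists three sensitivity analyses on investigator-assessed PFS. The third is introduced with "An additional worst-case sensitivity analysis will be performed based on the ITT Set". It counts investigator progression, progression reported in follow-up, and death. It departs from the primary definition only where the investigator reports progressive disease (PD) and the IR does not confirm it:

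- KW-0761 arm: the event is kept, but "the progression date will be set to the last tumor assessment plus one day in the KW-0761 treatment arm".
- Vorinostat arm: the subject is censored.

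No rule covers PD that only the IR finds, or PD that both find but the IR dates earlier. IR dates enter the separate secondary analysis of PFS by IR (SAP 6.11.2.4, Table 14.2.1.8), where they are used in both arms.

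**The concern.** With an unblinded assessor, two kinds of assessment bias would favour KW-0761. Investigators may call PD too readily on vorinostat, or they may miss it or call it late on KW-0761. SA3 addresses the first by censoring unconfirmed vorinostat PD. It does nothing about the second, so a missed or late KW-0761 call passes through unchanged.

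The date assigned to unconfirmed KW-0761 PD is a lesser problem. An on-treatment PD is itself called at a tumor assessment. If the last assessment is that one or a later one, adding a day moves the event after the investigator's date and puts no pressure on that arm.

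What is at stake is how the result can be described. A report could say that the treatment effect survived a worst case when the late-call bias in the KW-0761 arm was never tested.

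**Working it through.** **Design figures first.** The SAP gives "the reference median PFS for vorinostat is assumed to be 169 days", "The median PFS for KW-0761 therapy is targeted for 254 days", "a total of 255 PFS events will give 90% power", and a comparison "using a stratified Log-rank test at the one-sided 2.5% significance level".

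- HR = 169/254 = 0.665; ln HR = −0.4074.
- Schoenfeld events = 4(1.960 + 1.282)²/0.4074² = 254. Power at 255 events = 0.902.
- With 24 months' accrual and 12 months' follow-up, event probabilities are 0.929 and 0.840, so 288 subjects yield 144 × (0.929 + 0.840) = 254.8 events.

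The plan's 255 events and 288 subjects are reproduced. Nothing below changes them.

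**What the last tumor assessment means.** Sensitivity Analysis 1, in the same section, uses the phrase for the final assessment on record. So does the end-of-study rule in SAP 6.11.1.1: "the PFS time will be censored at the date of the last post-baseline tumor assessment". Where the SAP wants an assessment before some event, as in the new-anticancer-therapy rule of 6.11.1.1, it says so; SA3 does not. Usage therefore favours the final assessment, but the text does not settle it. The shift from the investigator's date is:

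- Final assessment, PD called there: +1 day.
- Final assessment, questionable PD confirmed at least 4 weeks later (6.11.1.1 keeps the initial date): at least 28 + 1 = +29 days.
- Assessment before the PD visit, skin or blood every 4 weeks: −28 + 1 = −27 days.
- Assessment before the PD visit, 8-weekly CT: −56 + 1 = −55 days.
- PD reported only in follow-up, if the rule covers it: earlier on either reading.

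**Effect on the hazard ratio.** This was simulated with 300,000 subjects, exponential PFS at the plan's medians, PD detected on a 4-weekly grid, and an unstratified Cox model. On that grid the primary HR is 0.681. The documents give no discordance rates, so the following are assumptions: 10% to 40% of investigator PD unconfirmed, equally in both arms; and 10% or 20% of KW-0761 subjects with an IR-earlier PD (by 56 days) or, if event-free, an IR-only PD.

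At 20% unconfirmed, the components taken separately are:

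- KW-0761 date rule alone: 0.678 (+1 day), 0.665 (+29), 0.690 (−27), 0.702 (−55).
- Vorinostat censoring alone: 0.850.
- Unconfirmed PD censored in both arms: 0.680, so the asymmetry between arms produces the shift.

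The full analysis gives:

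| Unconfirmed | SA3, PD visit +1 day | SA3, previous visit +1 day | previous column plus IR-only/earlier PD in 10% of KW-0761 | same, 20% |
|---|---|---|---|---|
| 10% | 0.755 | 0.763 | 0.787 | 0.813 |
| 20% | 0.845 | 0.862 | 0.890 | 0.918 |
| 30% | 0.961 | 0.990 | 1.022 | 1.055 |
| 40% | 1.115 | 1.160 | 1.198 | 1.236 |

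Counting the omitted KW-0761 events adds between 0.787 − 0.763 = 0.024 and 1.236 − 1.160 = 0.076. Re-dating from the PD visit to the previous visit adds between 0.763 − 0.755 = 0.008 and 1.160 − 1.115 = 0.045. The two kinds of discordance were drawn independently, so some KW-0761 subjects carry both, which slightly overstates the added shift.

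**The case against.** The strongest reply is that SA3 is already severe. Unconfirmed PD stays an event for KW-0761 and is removed for vorinostat. At 40% unconfirmed this alone takes the HR above 1. In a trial-sized simulation (317 subjects, the plan's medians, 10% unconfirmed per arm), SA3 as written was significant in only 67% of trials. This stands. A reader might infer that SA3 is a soft test, or that it leans towards KW-0761. It does not, because the comparison as a whole moves against KW-0761 on every reading.

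A reader might also infer that SA3 certainly dates KW-0761 events later than the investigator, or much later. The documents do not support that. The phrase is undefined, the worst-case label fits the earlier-dating reading, and PD reported in follow-up would move earlier. A subject with PD may stay on only for a questionable finding, and only until the next evaluation (SAP 3.2.2.3).

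Third, IR-only and IR-earlier PD do count in PFS by IR. True, but that analysis uses IR dates for both arms. No planned analysis takes the earlier of the two dates for KW-0761.

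Finally, the IR receives the investigator's mSWAT, which should limit disagreement in skin. That applies to unconfirmed PD and to IR-only PD alike, and is one reason the assumed rates are uncertain.

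**Conclusion.** The point holds as a labelling and specification defect in a supportive analysis. SA3 is not a worst case, because it tests one direction of disagreement and omits the one that would flatter KW-0761 within its own arm. This follows from the text and needs no assumption.

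The dating rule is a secondary fault. It is ambiguous, and on the more natural reading it adds no stress in the KW-0761 arm, but by itself it moves the HR only from 0.681 to somewhere between 0.665 and 0.702 at 20% unconfirmed.

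The omitted events are worth about 0.02 to 0.08 on the HR scale. That size rests on assumed discordance rates, exponential PFS, a 4-weekly grid and an unstratified model, so it shows direction and relative size and is not a forecast. The primary analysis, its significance level and the 255-event target are untouched. The change should be made, but the trial's main conclusion does not depend on it.

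**What to change.** In SAP 6.11.2.2 and the Table 14.2.1.4 footnote, rewrite the KW-0761 rule:

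- (a) An investigator PD not confirmed by the IR is an event on the day after the last tumor assessment before the assessment at which PD was called. If there was no earlier post-baseline assessment, use the day after randomization. State whether PD reported only in follow-up is covered.
- (b) PD called only by the IR is an event on the IR date. When both call PD, use the earlier date.

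Keep the vorinostat censoring as written. If the sponsor prefers not to add these rules, remove the worst-case label from the section and from the Table 14.2.1.4 title, and still define the last tumor assessment.

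The cost is a few lines of text and programming. Both sets of dates are already planned for Listings 16.2.6.16 and 16.2.6.17. The downside is a less favourable SA3 hazard ratio: about 0.02 to 0.08 higher from (b) under the assumed rates, plus a smaller amount from (a) if the final-assessment reading was the one intended.

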6.11.2.3 Analyses of Key Secondary Efficacy Variables

There are four key secondary endpoints in this study that require a comparison between treatment arms: ORR as assessed by the Investigator, changes in Skindex-29 score, FACT-G total score, and EQ-5D-3L index score. All assessments up to 6-months will be of interest for this analysis.

ORR as assessed by the Investigator will be compared between the 2 treatment arms using Cochran-Mantel-Haenszel (CMH) test adjusted for disease type, disease stage, and region. Additional analyses may be performed adjusting for treatment and other baseline characteristics. The exact 95% confidence intervals for ORR will be calculated for each treatment arm along with the difference in response rates between the two treatment arms. All 95% confidence intervals on individual rates will be computed using exact computational methods. Any confidence interval on the difference of proportions will be computed using exact unconditional confidence limits for the risk difference. These confidence intervals can be constructed using SAS[®] version 9.3 with the FREQ procedure specifying the RISKDIFF option in the EXACT statement.¹⁰ In addition to the results described above, the number and percentage of subjects achieving objective response (CR or PR) will be presented for each treatment arm.

The treatment differences in the mean change of Skindex-29 score from baseline across each planned timepoint (end of cycle 1, cycle 3, cycle 5) up to 6 months of assessments will be tested using a repeated measures mixed effects model with time, region, disease type, disease stage, treatment, and time-by-treatment interaction as factors and baseline score as a covariate. Restricted Maximum Likelihood (REML) method will be used. An unstructured covariance matrix will be employed to model the correlation among repeated measurements.

Appropriate contrasts will be used to determine the difference between the Vorinostat treatment group and the KW-0761 treatment group across the end of Cycles 1, 3, and 5. In case of convergence problems, another variance-covariance structure will be considered. The selection of any of these structures will be determined after exploration of the observed correlation structure. Least squares (LS) means, corresponding standard errors, 95% two-sided confidence intervals will be presented for the within-group change for odd cycles. For the between-treatment group comparison, the difference in LS means, corresponding standard errors, 95% two-sided confidence intervals, and two-sided p-value will also be derived from this ANCOVA model and presented for the odd cycles. This mixed-effects model will also be used to compare the treatment differences in the mean changes in Skindex-29 score from baseline to each scheduled time point at end of cycle 1, cycle 3, and cycle 5. In addition to

the Skindex-29 score, a Skindex score based on a subset of Skindex questions may be analyzed in a similar fashion.¹¹

Standard model diagnostics will be performed to assess the validity of the proposed ANCOVA model. These diagnostics will include an examination of the residuals for normality and homoscedasticity as well as testing for the significance of the treatment by baseline interaction term. If the residuals are not normally distributed, then the analysis will be carried out using Wilcoxon rank sum test instead.

In addition to the analysis described above, summary statistics including n, mean, standard deviation, median, minimum, and maximum will be provided for Skindex-29 score at baseline and each scheduled time point and change in total score at each of these scheduled assessments for each treatment arm.

The same methods described above for the analysis of change in Skindex-29 score will be performed for the analysis of change from baseline for the ends of cycle 1,3, and 5 in FACT-G total score and EQ-5D-3L index score.

Comparisons of these four key secondary endpoints between the two treatment arms will be conducted using p-values that are adjusted to control the overall study-wise Type 1 error rate to be less than 0.05. The four statistical tests that will be conducted are:

- ORR as assessed by the Investigator,
- Change in Skindex-29 score at through the 6-month assessment,
- Change in FACT-G total score at through the 6-month assessment, and
- Change in EQ-5D-3L index score at through the 6-month assessment.

Since these tests are not independent, the four key secondary tests will be conducted using the Sidak adjusted p-value method defined as:

Adjusted p-value = $1-(1-p)^4$ where **p** is the original p-value of the individual test.

These adjusted p-values will then be compared to .05 for each test.

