6.11.1.2.2 Changes in Skindex-29, FACT-G, and EQ-5D-3L from Baseline

The Skindex-29 is a validated instrument to measure the effect of skin disease on health-related quality of life.⁶ It is composed of 29 items assessing three domains: emotions, symptoms, and functioning. The items are scored on a 5-point Likert-type scale (never, rarely, sometimes, often, all the time). Responses to each item are transformed to a linear scale of 100 (never=0, rarely=25, sometimes=50, often=75, all the time=100) for the purpose of scale score calculation. A scale score is the mean of a subject's responses to the items in a given scale and the composite Skindex-29 score is calculated as the average of the 3 scale scores to measure the overall impact on quality of life. Higher scores indicate a higher impact of skin disease.

The FACT-G is a validated instrument for assessing health-related quality of life in subjects with cancer.⁷ The FACT-G consists of 27 items in the following 4 domains: physical

well-being (PWB), social/family well-being (SWB), emotional well-being (EWB), and functional well-being (FWB). The total FACT-G score is obtained by summing individual subscale scores. Response scores on negatively-phrased questions are reversed before summing. Higher scores for the scales and subscales indicate better quality of life.

The EuroQol/EQ-5D is a standardized, reliable and validated instrument to measure health-related quality of life. The EQ-5D self-reported questionnaire includes the EQ-5D descriptive system and a visual analog scale (VAS). The EQ-5D 3 level version (EQ-5D-3L) descriptive system comprises the following dimensions: mobility, self-care, usual activities, pain/discomfort and anxiety/depression. Each dimension has 3 levels: no problems, some problems, extreme problems. The EQ-5D index score is calculated based on the descriptive system using a set of item weights (value sets) to derive a single score ranging from -0.109 to 1, with 1 representing full health. The value sets for the US will be used for the calculation of the EQ-5D index score.⁸ The EQ-5D self-reported questionnaire also includes a visual analog scale (VAS), which records the respondent's self-rated health status on a graduated (0-100) scale, with 100 = best imaginable health state and 0 = worst imaginable health state.

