For the Pruritus Evaluation Likert Scale data, the changes in the Likert Scale score from baseline at different timepoints up to the cycle 11 assessments during the randomized treatment period will be analyzed using Wilcoxon rank sum test. The treatment difference in the median change of the Likert Scale score from baseline will be estimated using the Hodges-Lehmann estimate and a two-sided 95% confidence interval for the treatment difference will be obtained using the method of Moses.

All quality of life measurements and changes from baseline will be summarized descriptively at each scheduled time point.

For subjects who cross over from the vorinostat arm to the KW-0761 arm, ORR during the crossover portion of the trial will be estimated in a similar fashion as described above for ORR of the randomized therapy. In addition, the quality of life assessments during the crossover portion will be measured at the end of the first cycle after the first day of dosing for KW-0761. Baseline measurements for the crossover portion are considered to be those taken at the last assessment point of the previous cycle. The quality of life measurements as well as the changes from baseline during the crossover portion of the trial will be summarized descriptively. All summaries for the crossover portion will be purely descriptive. No statistical comparisons will be made for data collected during the crossover portion.

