Note: LS mean, SE, 95% CI and P-value are from MMRM with treatment, disease stage, and region as fixed effects and baseline score as a covariate. Adjusted P-value is calculated using Sidak method for the overall difference across time points through 6-month assessment (including End of Cycles 1, 3, and 5 timepoints only). Time points beyond Cycle 11 are not included due to the small number of subjects on study after cycle 11.

<<Programming Note: Repeat for Symptoms Scale Score, Emotions Scale Score, and Functioning Scale Score. Adjusted p-value is only presented for the overall treatment difference through 6-month assessment for the Skindex-29 score including the End of Cycle 1, End of Cycle 3, and End of Cycle 5 time points.>>

The following tables will have similar layout as Table 14.2.3.1 and Table 14.2.3.2:

Table 14.2.3.3
Summary of Skindex-29 Score and Change from Baseline by Visit During Randomized Treatment Period
Efficacy Evaluable Set

Table 14.2.3.4
Analysis of Change in Skindex-29 Score from Baseline During Randomized Treatment Period
Efficacy Evaluable Set

Table 14.2.3.5
Summary of Skindex-29 Score and Change from Baseline by Visit During Crossover Portion
Intent-to-Treat Set
Subjects Who Are Randomized to Vorinostat and Crossed Over to KW-0761

<<Programming Note: For tables 14.2.3.3 and 14.2.3.5, all scheduled timepoints according to the study procedures will be presented. >>

The following tables will have similar layout as Table 14.2.3.1 and Table 14.2.3.2:

Table 14.2.4.1
Summary of FACT-G Total Score and Change from Baseline by Visit During Randomized Treatment Period
Intent-to-Treat Set

Table 14.2.4.2
Analysis of Change in FACT-G Total Score from Baseline During Randomized Treatment Period
Intent-to-Treat Set

Table 14.2.4.3
Summary of FACT-G Total Score and Change from Baseline by Visit During Randomized Treatment Period
Efficacy Evaluable Set

Table 14.2.4.4
Analysis of Change in FACT-G Total Score from Baseline During Randomized Treatment Period
Efficacy Evaluable Set

Table 14.2.4.5
Summary of FACT-G Total Score and Change from Baseline by Visit During Crossover Portion
Intent-to-Treat Set
Subjects Who Are Randomized to Vorinostat and Crossed Over to KW-0761

Table 14.2.4.6
Summary of FACT-G Physical Well-Being Score and Change from Baseline by Visit During Randomized Treatment Period
Intent-to-Treat Set

Table 14.2.4.7
Summary of FACT-G Social Well-Being Score and Change from Baseline by Visit During Randomized Treatment Period

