Summary of Pruritus Evaluation Itchy Quality of Life Score and Change from Baseline by Visit During Crossover Portion
Intent-to-Treat Set
Subjects Who Are Randomized to Vorinostat and Crossed Over to KW-0761

<<Programming Note:

(1) Only the overall score will be presented for Itchy Quality of Life.

(2) For tables 14.2.7.1, 14.2.7.3, and 14.2.7.5, all scheduled timepoints according to the study procedures will be presented.>>

The following table will have a similar layout as Table 14.2.3.1:

Table 14.2.8.1
Summary of Pruritus Evaluation Likert Scale Score and Change from Baseline by Visit During Randomized Treatment Period
Intent-to-Treat Set

<<Programming Note: For Table 14.2.8.1, add a row in each time point to display interquartile range after median.>>

Table 14.2.8.2
 Analysis of Change in Pruritus Evaluation Likert Scale Score from Baseline
 During Randomized Treatment Period
 Intent-to-Treat Set

Time Point Treatment	N*	-----Change from Baseline-----				--Treatment Difference (KW-0761 vs. Vorinostat)--		
		--Baseline-- Median (IQR)	--Endpoint-- Median (IQR)	Median (IQR)	95% CI	Median (IQR)	95% CI	P-value
End of Cycle 1								
Vorinostat	xxx	xx.x (xx.xx)	xx.x (xx.xx)	xx.x (xx.xx)	(xx.x, xx.x)	xx.x (xx.xx)	(xx.x, xx.x)	x.xxxx
KW-0761	xxx	xx.x (xx.xx)	xx.x (xx.xx)	xx.x (xx.xx)	(xx.x, xx.x)			
End of Cycle 3								
Vorinostat	xxx	xx.x (xx.xx)	xx.x (xx.xx)	xx.x (xx.xx)	(xx.x, xx.x)	xx.x (xx.xx)	(xx.x, xx.x)	x.xxxx
KW-0761	xxx	xx.x (xx.xx)	xx.x (xx.xx)	xx.x (xx.xx)	(xx.x, xx.x)			
End of Cycle 5								
Vorinostat	xxx	xx.x (xx.xx)	xx.x (xx.xx)	xx.x (xx.xx)	(xx.x, xx.x)	xx.x (xx.xx)	(xx.x, xx.x)	x.xxxx
KW-0761	xxx	xx.x (xx.xx)	xx.x (xx.xx)	xx.x (xx.xx)	(xx.x, xx.x)			

Etc.

* N is the number of subjects with values at baseline and post-baseline.

Note: Treatment difference (KW-0761 - Vorinostat) and its 95% CI are estimated using Hodges-Lehmann estimator and Moses method.

P-values are obtained from Wilcoxon Rank Sum test. Time points beyond Cycle 11 are not included due to the small number of subjects on study after cycle 11.

The following tables will have similar layout as Table 14.2.8.1 and Table 14.2.8.2:

Table 14.2.8.3
Summary of Pruritus Evaluation Likert Scale Score and Change from Baseline by Visit During Randomized Treatment Period
Intent-to-Treat Set

Table 14.2.8.4
Analysis of Change in Pruritus Evaluation Likert Scale Score from Baseline
During Randomized Treatment Period
Intent-to-Treat Set

Table 14.2.8.5

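### A normality check with no criterion replaces the confirmatory mixed-model test for three key secondary quality-of-life endpoints with a Wilcoxon test that has no rule for combining visits

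*SAP*

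**What the plan says.** SAP 6.11.2.3 specifies for change in Skindex-29 a "repeated measures mixed effects model with time, region, disease type, disease stage, treatment, and time-by-treatment interaction as factors and baseline score as a covariate". It is fitted by REML with an unstructured covariance, and treatment is tested by a contrast across the ends of Cycles 1, 3 and 5. The section carries the same methods over to FACT-G total score and the EQ-5D-3L index. With investigator-assessed ORR these make a family of four, and "the four key secondary tests will be conducted using the Sidak adjusted p-value method", that is, 1 − (1 − p)^4 compared with 0.05. The footnote to the Table 14.2.3.2 shell attributes the p-values to the mixed model and states: "Adjusted P-value is calculated using Sidak method for the overall difference across time points through 6-month assessment".

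The same section asks for the residuals to be examined for normality and equal variance, and then says: "If the residuals are not normally distributed, then the analysis will be carried out using Wilcoxon rank sum test instead".

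Wilcoxon appears in three other places in the SAP:

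- **6.11.2.4, Itchy QoL and EQ-5D VAS.** A similar fallback applies on a significant departure from the assumptions. No test, level or visit rule is given.
- **6.11.2.4, Likert scale.** Changes "from baseline at different timepoints up to the cycle 11 assessments during the randomized treatment period will be analyzed using Wilcoxon rank sum test". The Table 14.2.8.2 shell has separate results for each visit, with the footnote "P-values are obtained from Wilcoxon Rank Sum test".
- **8.2.5.** Sample Wilcoxon code, labelled for the Likert score, has treatment as the class and the change score as the variable. It has no visit, stratum or baseline term.

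Protocol 10.3 names repeated measures ANCOVA through six months for these endpoints and mentions no rank-test fallback.

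**The concern.** The fallback is a replacement, not a sensitivity analysis, and it covers three of the four multiplicity-controlled secondary claims. Two things needed to carry it out are missing: when it applies, and what single quantity per subject is ranked. Two analysts following the section on the same data could run different tests and reach different conclusions.

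Timing makes this worse. The residuals in question are those of a model that includes treatment, in an open-label trial. The model must be fitted before the switch is decided, so whoever judges normality can already see the mixed-model result. Finalising the SAP before database lock does not remove that.

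The switch also changes what is tested. It drops baseline score as a covariate (change from baseline is still the variable), drops adjustment for disease type, stage and region, and loses the mixed model's likelihood-based use of subjects with missing visits.

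**Working it through.** **1. The plan's own figure.** Inputs from SAP 6.11.2.3: family level 0.05, four tests, Sidak. The level per test is 1 − 0.95^(1/4) = 0.01274. In reverse, 1 − (1 − 0.01274)^4 = 0.0500. The formula is right, and it needs exactly one p-value per endpoint.

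**2. What the text determines.**

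| Element | Mixed model | Wilcoxon fallback |
|---|---|---|
| When used | default | residuals not normal; no test, level, plot rule or residual type |
| Quantity | contrast over Cycles 1, 3, 5 | not stated |
| Adjustment | baseline, disease type, stage, region | none stated |
| Missing visits | likelihood-based | not stated |
| Sidak-adjusted result in shell | yes, overall difference | no layout |

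The other Wilcoxon text does not fill the right-hand column. It is either by visit for another scale, or equally undefined.

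**3. The trigger.** The EQ-5D index is a "single score ranging from -0.109 to 1, with 1 representing full health", so a ceiling is plausible. In four simulated capped scenarios (step 4), Shapiro-Wilk at 0.05 fires in 84 to 100% of trials, |skewness| > 0.5 in 0.5 to 96%, and |skewness| > 1 in about 0%. With normal scores Shapiro-Wilk fires in 5%. The unstated criterion therefore decides the test.

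**4. Power.** The documents give no QoL SD, effect or correlation. Assumed:

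- 158 per arm (317/2, rounded down), SD 20, effect 6 points, between-visit correlation 0.5 to 0.7.
- For the capped score: limits −0.109 and 1, SD 0.20, shift 0.06, latent mean 0.75 or 0.85.
- QoL observed until progression, independent of score. At the plan's medians, observed at day 5 × 28 = 140: exp(−ln2 × 140/169) = 0.563 and exp(−ln2 × 140/254) = 0.682.
- Two-sided 0.01274 and 2,000 replicates per scenario.

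| Scores (correlation) | Mixed model % | Wilcoxon, mean change % | Wilcoxon, Cycle 5 only % | Whole rule, Shapiro-Wilk % |
|---|---|---|---|---|
| Normal (0.5) | 87.5 | 66.2 | 30.7 | 86.4 |
| Normal (0.6) | 91.3 | 76.8 | 40.5 | 90.6 |
| Normal (0.7) | 95.4 | 88.3 | 55.6 | 95.0 |
| Capped, mean 0.75 (0.5) | 84.1 | 58.1 | 28.1 | 58.2 |
| Capped, mean 0.75 (0.7) | 93.3 | 82.3 | 46.6 | 83.9 |
| Capped, mean 0.85 (0.5) | 82.3 | 53.2 | 24.0 | 53.2 |
| Capped, mean 0.85 (0.7) | 91.7 | 74.7 | 37.6 | 74.7 |
| t(5) (0.5) | 87.8 | 77.4 | 43.8 | – |
| t(5) (0.7) | 96.3 | 95.5 | 68.9 | – |
| t(3) (0.5) | 88.3 | 94.5 | 64.0 | – |
| t(3) (0.7) | 96.4 | 99.7 | 88.0 | – |
| 10% outlying visits (0.5) | 84.6 | 71.6 | 36.6 | – |
| 10% outlying visits (0.7) | 84.9 | 89.7 | 62.0 | – |

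In the last six rows Shapiro-Wilk fires in over 99% of trials, so the rule is practically the Wilcoxon result.

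Cost of the rule (mixed model minus whole rule):

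- Normal: 1.1, 0.7 and 0.4 points.
- Capped, Shapiro-Wilk: 25.9, 9.4, 29.1 and 17.0 points.
- Capped, |skewness| > 0.5 (whole-rule power 82.5, 93.2, 54.1, 83.8%): 1.6, 0.1, 28.2 and 7.9 points.

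The mixed model and Wilcoxon on the mean change disagree on significance in 4 to 33% of trials.

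**5. Level.** Over 13 null scenarios of 6,000 replicates (simulation SE about √(0.01274 × 0.98726/6000) = 0.14 points): mixed model 1.12–1.42%; Wilcoxon on the mean change 1.03–1.43%; Shapiro-Wilk rule 1.03–1.43%; skewness rule 1.13–1.53%. All are close to 1.27%. If the smaller of the mixed-model and Wilcoxon p-values is taken, the level is 1.97–2.40% per endpoint. Were that done for all three QoL endpoints, the family error would be 1 − (1 − a)^3 × (1 − 0.01274), which is 0.070 at a = 0.0197 and 0.082 at a = 0.0240. That treats the four tests as independent, which the SAP itself says they are not.

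**The case against.** The best defence is that these endpoints are secondary, that an experienced statistician would fix the details sensibly, and that any rule fixed in advance holds its level. The last part stands, as step 5 shows. It also stands that always-Wilcoxon against always-mixed-model is not the effect of the rule: with near-normal scores the rule rarely fires and costs almost nothing. The large losses need both a capped distribution and a sensitive trigger, and with heavy tails the rank test can win. Finally, a stated criterion plus one per-subject summary would also close the gap, so dropping the fallback is the simpler remedy rather than the only one.

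A reader might go further and infer that any of the three by-visit Wilcoxon results could carry the claim. The shell excludes this: the adjusted p-value belongs only to the overall difference through six months. If it were done anyway, the bound under independence is 1 − (1 − 0.01274)^3 = 0.0377 per endpoint and, for ORR plus nine tests, 1 − (1 − 0.01274)^10 = 0.120. Nor do the documents support reading the sample code as an instruction to stack all visits in one rank sum test. It is labelled for the Likert score, which the SAP analyses at separate timepoints.

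What remains is that nothing in either document states the trigger or the ranked quantity.

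**Conclusion.** The point holds as a failure to determine in advance the confirmatory test for Skindex-29, FACT-G and the EQ-5D-3L index. That conclusion rests on the text alone and needs no simulation. It is not a finding that type I error is inflated: that happens only if the choice follows the results. Nor is it a finding that Wilcoxon is generally weaker.

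The sizes are illustrative and rest on an assumed SD, effect, correlation and score-independent dropout. The rule costs about 1 point of power or less with normal scores and roughly 10 to 30 points with capped scores under Shapiro-Wilk. In the t(3) scenarios Wilcoxon gains 3 to 6 points. Choosing the smaller p-value gives about 2.0 to 2.4% per endpoint instead of 1.27%. The primary PFS test and ORR are untouched. It should be changed because the repair is cheap.

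**What to change.** 1. In SAP 6.11.2.3, delete the substitution sentence for the three key secondary QoL endpoints. State that the mixed-model contrast over the ends of Cycles 1, 3 and 5, with the factors listed in that section, is the sole Sidak-adjusted test for each endpoint, whatever the residual diagnostics show.
2. Correct the Table 14.2.3.2 footnote to match that model. It now omits disease type, time and the time-by-treatment interaction, although the text of 6.11.2.3 and the sample code in 8.2.5 include all three.
3. Report two analyses as sensitivity only: the same contrast with sandwich standard errors, and a van Elteren test on each subject's mean available change at the ends of Cycles 1, 3 and 5, stratified by disease type, stage and region.
4. Optional and minor: the covariance fallback is also left open ("The selection of any of these structures will be determined after exploration of the observed correlation structure"). Name a fixed order instead, with sandwich standard errors if a simpler structure is used. Unstructured fits converged in at least 99.6% of simulated trials, so this will seldom matter.

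The cost is SAP wording and two extra outputs per endpoint, with no new data. The downside is some lost power if scores prove heavy-tailed, about 3 to 6 points in the scenarios where Wilcoxon won.
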